RESEARCH PROPOSAL

Version 1

Date: January 8, 2015

1. General Information

Title:

A randomized double blinded study comparing the live birth rate of IVF treatment following brief incubation of oocytes and spermatozoa versus standard incubation

Principal Investigator:

[name] [name]

Clinical associate Professor, Center of Assisted Reproduction, Shanghai first Maternity and Infant health hospital, Tong Ji University

Co-Investigators:

[name] [name], [name], [name] [name], [name] [name], [name] [name],

Shanghai first Maternity and Infant health hospital, Tong Ji University

[name] [name]

Department of Obstetrics and Gynaecology, The University of Hong Kong

Correspondence to:

[name] [name], Center of Assisted Reproduction, Shanghai first Maternity and Infant health hospital, Tong Ji University

[name]

[contact]

Email : [contact]

2. Background

In vitro fertilization (IVF) treatment is now commonly used to treat infertile couples. During IVF treatment, oocytes and sperm are routinely incubated overnight and this may lead to suboptimal culture conditions because of increased reactive oxygen species (ROS) produced by sperm in the standard incubation [1]. High levels of ROS can adversely affect the quality of the embryos, result in hardening of the zona pellucida and impair the implantation capacity of embryos [2-4]. Studies shows successful fertilization of an oocyte occurs 20mins after the gametes are put together [5]. Sperm can penetrate through the cumulus cells within 15min, and 80% of oocytes can be fertilized when they are exposed to a large number of spermatozoa within 1hr

[1]. As an attempt to avoid possible detrimental effects on the oocytes from long exposure to sperm, the brief incubation insemination protocol was developed. It implies that prolonged incubation of oocytes and sperm may not be necessary and may even be harmful. Some reports suggest that a sperm-oocyte exposure time of 1–6 h improves IVF outcomes [1,2,6,7]. However, other studies report no such advantage with a short insemination time [8,9,10].

A recent meta-analysis shows [11] brief incubation of gametes was associated with significantly higher rates of clinical pregnancy (RR: 1.84, 95% CI: 1.24–2.73), ongoing pregnancy (RR: 1.73, 95% CI: 1.27–2.33) and higher rate of implantation (RR: 1.80, 95% CI: 1.43–2.26) than standard incubation. But the rates of normal fertilization (RR: 0.98, 95% CI: 0.93–1.02), good quality embryos (RR: 1.24, 95% CI: 1.0–1.53) and polyspermy (RR: 0.84, 95% CI: 0.7–1.01) were not significantly different compared with standard incubation.

In a Cochrane meta-analysis [12] eight RCTs with 733 women were included, and showed similar results. But it only reported clinical pregnancy rate and ongoing pregnancy rate which were significantly higher in brief incubation group than standard incubation. For the miscarriage rate, there were six miscarriages in one trial including 167 women. This low quality evidence suggested no significant difference in the odds of miscarriage between brief incubation and standard incubation (OR 1.98, 95% CI 0.35 to 11.09; P = 0.44). It is important to note that the live birth rate, which is the important outcome parameter, was not reported in all these studies. It is uncertain whether brief incubation improves the live birth rate compared with standard incubation.

Drawbacks inherent to the quality of these studies, such as lack of allocation concealment and no blinding, limit the quality of the available evidence.

3. Objectives:

The aim of this randomized double blinded study is to compare the live birth rate of IVF treatment following brief incubation of oocytes and sperm versus standard incubation. The hypothesis is that a brief incubation improves the live birth rate of IVF treatment.

4. Trial design:

Eligible patients will be recruited and randomized into one of the following two groups by computer-generated random numbers that will be placed in sealed envelopes:

1. Brief incubation group: oocytes will be exposed to spermatozoa for 2 hours
2. Standard incubation group: oocytes will be exposed to spermatozoa for 20 hours

5. Subject selection and exclusion

The target population for the trial will be women undergoing IVF treatment in our unit

5.1 Inclusion criteria:

- Women under 42 years of age
- Infertile for ≥ 1 year
- Indications for conventional insemination such as tubal, endometriosis, unexplained and mild male factor
- Written informed consent

5.2 Exclusion criteria:

- Women using donor eggs/donor sperm
- Women with abnormal uterine cavity shown on hysterosalpingogram or saline infusion sonogram
- Women with hydrosalpinges shown on scanning and not treated
- Husband with severe oligospermia or azospermia or teraspermia (normal morphology $< 5\%$)
- Previous fertilization failure for conventional insemination in the past (fertilization rate $< 30\%$)

6. Treatment of subjects

All techniques of IVF including ovarian stimulation will be provided according to local protocols.

6.1 Ovarian stimulation and IVF

All women will start their IVF treatment with ovarian stimulation using either the long agonist or antagonist protocols. For long protocol, gonadotropin-releasing hormone analogue (GnRHa) will be given for pituitary desensitization, on Day 2–3 of the menstrual cycle, they will undergo transvaginal ultrasound examination and serum E2 measurement. Human

menopausal gonadotrophin (hMG) or recombinant FSH will be given at 150–300 IU per day based on the antral follicle count, age of women and previous ovarian response, according to the standard operation procedures of the centre. Ovarian response will be monitored by serial transvaginal scanning with or without hormonal monitoring. Further dosage adjustments will base on the ovarian response at the discretion of the clinicians in charge. For antagonist protocols, antagonist (cetritide 0.25mg daily) will be given on the 6th day of ovarian stimulation until the day of hcg trigger.

When three leading follicles reach ≥ 18 mm, hCG 10 000 IU or ovidrel 250 mg will be given to trigger final maturation of oocytes. Oocyte retrieval will be arranged around 36 h later.

6.2 Insemination Procedures

All semen samples were prepared by the conventional swim-up procedure. At 2hr after oocyte retrieval, each matured oocyte will be inseminated with approximately 50,000–100,000 motile spermatozoa.

6.3 Assignment and masking

On the day of OPU, patients will be randomized after oocyte pick up by a laboratory technician according to a computer generated randomization list in sealed envelopes into the brief incubation group or the standard incubation group. Until the completion of the whole study, both the patients and the clinicians were blinded to the group assigned.

Control arm

Women who allocated to the standard incubation group, all oocytes will be exposed to spermatozoa for 20 hours, and checked for fertilization on day 1 (20 hours) after denuding

Intervention arm

For those allocated to the brief incubation group, all oocytes will be exposed to spermatozoa for 2 hours and gently washed through two organ dishes containing 1.5 ml of equilibrated medium, and then transferred to the corresponding microdroplet of equilibrated fresh medium. Surrounding cumulus cell will be retained, not removed from the oocytes.

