Outcomes for participants will be analysed in the groups to which they are assigned regardless of deviation from the protocol or treatment received (intention-to-treat). Comparative statistical analysis will entail calculating the relative risk (RR) (95% CI) for the primary outcome (99% CIs for all dichotomous secondary outcomes), the mean difference (99% CI) for normally distributed continuous secondary outcomes, or the median difference (99% CI) for skewed continuous variables.

All analyses will adjust for the minimisation factors to account for the correlation between treatment groups introduced by balancing the randomisation (which forces outcomes between treatment arms to be similar apart from any treatment effect).

Adjusted risk ratios will be estimated using a log binomial regression model, or using a log Poisson regression model with a robust variance estimator if the binomial model fails to converge. Linear regression will be used for normally distributed outcomes and quantile regression for skewed continuous variables.

Pre-specified subgroup analyses will include (i) Natural versus hormone replacement frozen replacement cycles, and (ii) Cleavage versus blastocyst stage transfer.

9. Sample size estimation:

The average live birth rate in our center from 2010-2012 was 30% per transfer. According to the recent meta-analysis[11], briefincubation of gametes was associated with significantly higher rates of ongoing pregnancy (RR: 1.73, 95%CI: 1.27–2.33) than standard insemination.

Assuming live birth in the brief incubation group increase from 30% to 50% (increase by 70%); with 90% power and a two-sided 5% level of statistical significance, we will need to recruit 124 women in each arm. To account for 10% loss to follow up, we will recruit 140 subjects in each group or 280 subjects for the whole study.

10. Assessment of safety

Results from a recent meta-analysis [11,12] showed the rates of normal fertilization, good quality embryos and polyspermy were not significantly different with short time incubation of gametes compared with standard insemination. Thus, there should be no major safety concern in this study.

11. Direct access to source data / documents:

Trial-related monitoring, audits, IRB review and regulatory inspections are allowed.

12. Quality control and quality assurance

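### The time of the draw is fixed only as after oocyte pick-up, so the laboratory may know the arm during an insemination step that is common to both arms, and women never inseminated can be randomised

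*Protocol*

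**What the plan says.** All references are to the protocol.

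- **Draw (section 6.3).** "On the day of OPU, patients will be randomized after oocyte pick up by a laboratory technician". The list is produced by computer and held in sealed envelopes. The section does not say how long after pick-up the envelope is opened, or whether the person who opens it also inseminates.
- **Insemination (section 6.2), both arms.** "At 2hr after oocyte retrieval, each matured oocyte will be inseminated with approximately 50,000–100,000 motile spermatozoa".
- **Brief arm (section 6.3).** "all oocytes will be exposed to spermatozoa for 2 hours and gently washed through two organ dishes".
- **Standard arm (section 6.3).** "all oocytes will be exposed to spermatozoa for 20 hours, and checked for fertilization on day 1 (20 hours) after denuding".
- **Blinding (section 6.3).** "both the patients and the clinicians were blinded to the group assigned". Laboratory staff are not mentioned.
- **Analysis set (section 8.1).** "Outcomes for participants will be analysed in the groups to which they are assigned regardless of deviation from the protocol or treatment received (intention-to-treat").
- **Sample size (section 9).** 30% versus 50% live birth, 90% power, two-sided 5% level, 124 women per arm, raised to 140 per arm for 10% loss to follow-up. There is no allowance for women who are randomised but not conventionally inseminated.

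**The concern.** Good practice is to draw the allocation as late as the design allows, just before the arms part. Here two things can go wrong between pick-up and that moment.

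First, whoever judges which oocytes are mature and sets the sperm number may already know the arm. The protocol's background (section 2) says that rapid fertilisation is seen when oocytes meet a large number of sperm, and it attributes embryo harm to reactive oxygen species from sperm. By its title, reference 10 found less fertilisation after short co-incubation, and reference 6 links high sperm concentration to embryo viability and pregnancy rate. A technician who expects poorer fertilisation after 2 hours would have a reason to inseminate brief-arm oocytes near the top of the range. Sperm number would then be mixed with exposure time in the fertilisation, polyspermy and embryo-quality outcomes. The protocol does not expressly call for the sperm number per oocyte to be recorded, so the mixing might not be detectable afterwards. Section 2 itself criticises previous trials for weak concealment and absent blinding.

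Second, a woman may be randomised and then have no mature oocyte, no usable semen or a change of insemination method. She stays in the intention-to-treat set although the two arms never differed for her, and the treatment difference shrinks.

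**Working it through.** **1. Timing.** Retrieval is at 0 h. Insemination is at 2 h (section 6.2). The brief-arm wash comes after 2 h of exposure (section 6.3), so at 2 + 2 = 4 h. Until then both arms are handled alike. The draw could be made at any time up to about 4 h after retrieval without changing either arm.

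**2. Room for choice.** The sperm number per mature oocyte may lie between 50,000 and 100,000, a ratio of 100,000 / 50,000 = 2. A full two-fold difference between arms needs every brief-arm oocyte at one end and every standard-arm oocyte at the other. It is a ceiling, not an estimate.

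**3. The plan's own sample size.** With p1 = 0.30, p2 = 0.50, mean 0.40 and pooled variance:

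n = [1.960 × √(2 × 0.40 × 0.60) + 1.282 × √(0.30 × 0.70 + 0.50 × 0.50)]² / 0.20²

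= [1.960 × 0.6928 + 1.282 × 0.6782]² / 0.04 = 124 per arm.

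This matches section 9. Dividing by 0.90 gives 138, which the protocol rounds up to 140; 140 × 0.90 = 126 remain after the planned loss. No stated figure is disputed.

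**4. Dilution.** Let f be the share of randomised women who never reach the comparison. The protocol gives no value, so f is an assumption. Suppose these women have 30% live birth in both arms, for example after fertilisation by another method. Then

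p2 = 0.50 × (1 − f) + 0.30 × f, and

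power = Φ{[(p2 − 0.30) × √n − 1.960 × √(2 × m × (1 − m))] / √(0.21 + p2 × (1 − p2))}, with m = (0.30 + p2) / 2.

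For f = 0.05: p2 = 0.49 and m = 0.395. At n = 126, power = Φ{[0.19 × √126 − 1.960 × 0.6913] / 0.6782} = Φ(1.147) = 87.4%.

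| f (assumed) | Rates | Power, 126 per arm | Power, 140 per arm | n per arm for 90% |
|---|---|---|---|---|
| 0 | 30% v 50% | 90.5% | 93.1% | 124 |
| 2% | 30% v 49.6% | 89.3% | 92.2% | 129 |
| 5% | 30% v 49% | 87.4% | 90.6% | 138 |
| 10% | 30% v 48% | 83.8% | 87.4% | 153 |
| 20% | 30% v 46% | 74.7% | 79.1% | 192 |

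The 126 column adds these losses to the full 10% loss to follow-up. The 140 column assumes that every woman's outcome is known.

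If the women concerned have no live birth in either arm, both rates are multiplied by (1 − f). Power at 126 per arm is then 87.9% for f = 5%, 85.0% for 10% and 78.1% for 20%.

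**The case against.** The strongest reply is that the protocol does not say what a reader might infer from it, namely that the envelope is opened at pick-up and insemination is done with the arm known. The text says after pick-up, on the same day. A draw after insemination already complies. Nor does the text say that the same technician draws and inseminates, or that the sperm number is chosen woman by woman. This stands: the wording leaves the route open but does not describe anyone taking it.

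The motive to favour one arm is also weaker than a single study title suggests. The meta-analysis quoted in section 2 gives a relative risk for normal fertilisation of 0.98 (95% CI 0.93 to 1.02). The outcomes most directly affected are secondary, and for live birth the link to sperm number rests on little more than a reference title. These points lower the likely size of any effect. They do not close the route.

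On dilution, eligibility works against large losses. Women need an indication for conventional insemination, and severe male factor and previous fertilisation failure are excluded. Cycles cancelled before retrieval are never randomised. Keeping randomised women in the analysis is ordinary intention-to-treat practice, and a loss unrelated to allocation costs power without biasing the comparison. All of this stands, and the lowest power figures need both a sizeable assumed loss and the full 10% loss to follow-up on top.

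Finally, a later draw leaves much untouched. The wash reveals the arm to the laboratory, so fertilisation checks and embryo grading remain open to unmasked staff. That limits the benefit to the steps before the arms diverge, which a later draw can protect fully.

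**Conclusion.** The point holds as a cheap improvement to a loosely fixed step, not as a demonstrated bias. Section 6.3 allows the arm to be known during oocyte selection and insemination, although nothing in either arm requires it to be known before about 4 h after retrieval. It also lets women who are never conventionally inseminated enter the analysis set.

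A reader might go further and infer that sperm number will differ two-fold between arms, or that the trial is underpowered. The documents support neither. The two-fold figure is the worst case within the permitted range. The stated sample size reproduces, and any shortfall depends on a loss rate that is not given. With 30% live birth in both arms among the women lost, assumed losses of 5% or 10% give power of about 87% or 84% at 126 per arm, and about 91% or 87% if all 140 are analysed. At 2% or less, power stays at about 89% or above.

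Losses after exposure, such as failed fertilisation or no transfer, are a separate matter. They may be caused by the allocation and belong in the intention-to-treat analysis.

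**What to change.** Add to section 6.3: *The envelope is opened only after conventional insemination is complete and the sperm number per oocyte has been recorded, and shortly before the end of the first 2 hours of co-incubation. Women with no inseminated oocytes are not randomised, and their number is reported.*

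The draw should come shortly before the 2-hour point and not exactly at it, so that opening the envelope does not delay the brief-arm wash and lengthen that arm's exposure. It would help to have the envelope opened by someone who neither inseminates nor grades embryos.

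The cost is a short addition to the text, a later draw on the same day, and wash dishes and fresh-medium droplets made ready for every woman, since her arm is not yet known. Neither arm's exposure time changes. Masking of fertilisation checks and embryo grading would need its own provision.

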6.4 Fertilization and Embryo Evaluation

Both groups of oocytes will be decoronated and checked for the presence of two pronuclei and two polar bodies to confirm fertilization. All other

outcomes (i.e., no fertilization, one pronucleus, polyspermy, degeneration) will be recorded.

Embryo morphology will be assessed every day of culture. Embryos will be scored according to the following criteria. Briefly, embryos are classified as: grade A, no cellular fragmentation; grade B, <20% fragmentation; grade C, 20% to 50% fragmentation; and grade D, >50% fragmentation. The number of blastomeres per embryo was also recorded. Grade A and B embryos constituted the “good quality embryo”.

The transfer is performed by the team clinician with a maximum of 2 embryos being replaced according to the standard protocol under transabdominal ultrasound guidance. Luteal phase support is given at the discretion of the physician.

6.5 Follow up strategy:

A pregnancy test will be carried out 2 weeks after embryo transfer in both arms. All women who have a positive pregnancy test 2 weeks after a fresh embryo transfer will undergo a transvaginal ultrasound scan after a further 2 weeks to identify the presence of a gestation sac with a fetal heart signifying an ongoing pregnancy.

Data on all pregnancy outcomes including early pregnancy losses such as miscarriage or ectopic pregnancy will be collected.

In order to achieve consistency with respect to the collection of outcome, standardised case report forms (CRF) will be completed for each woman at each centre. These CRFs will include details on treatment received, pregnancy outcomes, complications in pregnancy, mode of delivery and birth outcomes.

7. Study outcomes

Primary outcome is the live birth rate.

Secondary outcomes:

- Miscarriage rate
- Clinical pregnancy rates
- Normal fertilization rate
- polyspermy rate(≥ 3 PN)
- Cleavage rate
- High quality embryo formation rate
- Implantation rate

8. Statistics

8.1 Analysis plan:

Demographic factors and clinical characteristics collected as part of baseline data collection will be summarised with counts (percentages) for categorical variables, mean (standard deviation [SD]) for normally distributed continuous variables, or median (interquartile [IQR] or entire range) for other continuous variables.

Outcomes for participants will be analysed in the groups to which they are assigned regardless of deviation from the protocol or treatment received (intention-to-treat). Comparative statistical analysis will entail calculating the relative risk (RR) (95% CI) for the primary outcome (99% CIs for all dichotomous secondary outcomes), the mean difference (99% CI) for normally distributed continuous secondary outcomes, or the median difference (99% CI) for skewed continuous variables.

All analyses will adjust for the minimisation factors to account for the correlation between treatment groups introduced by balancing the randomisation (which forces outcomes between treatment arms to be similar apart from any treatment effect).

Adjusted risk ratios will be estimated using a log binomial regression model, or using a log Poisson regression model with a robust variance estimator if the binomial model fails to converge. Linear regression will be used for normally distributed outcomes and quantile regression for skewed continuous variables.

Pre-specified subgroup analyses will include (i) Natural versus hormone replacement frozen replacement cycles, and (ii) Cleavage versus blastocyst stage transfer.

9. Sample size estimation:

The average live birth rate in our center from 2010-2012 was 30% per transfer. According to the recent meta-analysis[11], briefincubation of gametes was associated with significantly higher rates of ongoing pregnancy (RR: 1.73, 95%CI: 1.27–2.33) than standard insemination.

Assuming live birth in the brief incubation group increase from 30% to 50% (increase by 70%); with 90% power and a two-sided 5% level of statistical significance, we will need to recruit 124 women in each arm. To account for 10% loss to follow up, we will recruit 140 subjects in each group or 280 subjects for the whole study.

10. Assessment of safety

Results from a recent meta-analysis [11,12] showed the rates of normal fertilization, good quality embryos and polyspermy were not significantly different with short time incubation of gametes compared with standard insemination. Thus, there should be no major safety concern in this study.

11. Direct access to source data / documents:

Trial-related monitoring, audits, IRB review and regulatory inspections are allowed.

12. Quality control and quality assurance

Patients will be managed by the listed investigators who have adequate experience in managing assisted reproduction treatments. A Trial steering committee will be formed which will oversee the conduct of the trial.

13. Ethics

Written consent will be obtained from all patients. The patient information sheet and consent forms in English and Chinese are enclosed. Ethics approval will be obtained from the Institutional Review Board, Shanghai first Maternity and Infant health hospital Hospital.

14. Data Handling and record keeping

All data will be stored for three years. A designated research nurse will be responsible for data management including data coding, monitoring and verification.

15. Financing and insurance

The study will be funded somewhere this year pending to be applied.

16. Publication policy

The findings of this study will be submitted for consideration for publication in peer-reviewed scientific journal.

17. Supplements

The study will be conducted in compliance with the Declaration of Helsinki and Good Clinical Practice (ICH-GCP)

18. We certify that the information given is complete and accurate to the best of our knowledge.

Reference:

- [5] Wassarman PM. Fertilization in mammals. *Sci Am* 1988, 259: 78-84
- [6] Gianaroli L, Fiorentino A, Magli MC, Ferraretti AP, Montanaro N. Prolonged sperm-oocyte exposure and high sperm concentration affect human embryo viability and pregnancy rate. *Hum Reprod* 1996b;11:2507 – 2511.

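### Five secondary outcomes are counted over several oocytes or embryos per woman, but section 8.1 sets no unit of analysis and its risk-ratio models do not allow for correlation within woman

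*Protocol*

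**What the plan says.** Protocol section 6.3 makes the woman the unit of randomisation: "patients will be randomized after oocyte pick up by a laboratory technician". The whole cohort of her oocytes then follows her arm. In the intervention arm "all oocytes will be exposed to spermatozoa for 2 hours and gently washed"; in the control arm "all oocytes will be exposed to spermatozoa for 20 hours, and checked for fertilization on day 1".

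Section 7 lists seven secondary outcomes. Miscarriage and clinical pregnancy are events of the woman. The other five are by nature counted over oocytes or embryos: "Normal fertilization rate", polyspermy, cleavage, high-quality embryo formation and "Implantation rate". No denominator is given for any of them.

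Section 8.1 offers two routes. Dichotomous outcomes get a relative risk, with "99% CIs for all dichotomous secondary outcomes". The model is specified as follows: "Adjusted risk ratios will be estimated using a log binomial regression model, or using a log Poisson regression model with a robust variance estimator", where the Poisson version is reserved for non-convergence of the binomial one. Continuous secondary outcomes get a mean or median difference with a 99% interval, by linear or quantile regression. The only correlation the section addresses is the one it attributes to balancing the randomisation.

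**The concern.** Oocytes from one couple share the sperm sample, the ovarian response and the culture conditions, so their results tend to be alike. A model that counts each oocyte as an independent observation credits the trial with more information than it has. The interval is then too narrow, and a chance difference between arms is too easily taken as real.

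The 99% level is the only guard that section 8.1 states for the secondary outcomes, and it would be weakened for the laboratory rates. These rates also matter beyond description. Section 10 rests its safety statement on normal fertilisation, good-quality embryos and polyspermy not differing significantly in earlier work. Intervals that are too narrow on the same outcomes here could signal a false difference, or give more reassurance than the data support.

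**Working it through.** **The plan's own figure.** Section 9 assumes 30% against 50%, 90% power and a two-sided 5% level. With the pooled-variance formula, n per arm = [1.960·√(2·0.4·0.6) + 1.282·√(0.3·0.7 + 0.5·0.5)]² / 0.20² = (1.358 + 0.869)² / 0.04 = 124.0. The stated 124 reproduces. Allowing for 10% loss, 124/0.90 = 137.8, so 138 against the stated 140. This calculation is for live birth, with one result per woman, so clustering of oocytes does not enter it.

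**Inputs for the five rates.** From the protocol: randomisation by woman, a nominal level of 99%, and at most two embryos transferred (section 6.4). Not in the protocol: the number of oocytes or embryos per woman, m, and the intraclass correlation, ICC. I assume m = 5 to 12 and ICC = 0.05 to 0.30. For implantation I take m = 2.

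**Formulas.** Design effect DE = 1 + (m − 1)·ICC. The unclustered standard error is too small by a factor of √DE. Actual coverage of a nominal 99% interval = 2Φ(2.576/√DE) − 1.

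| m | ICC | DE | √DE | Coverage |
|---|---|---|---|---|
| 2 | 0.05 | 1.05 | 1.02 | 98.8% |
| 2 | 0.30 | 1.30 | 1.14 | 97.6% |
| 5 | 0.05 | 1.20 | 1.10 | 98.1% |
| 5 | 0.30 | 2.20 | 1.48 | 91.8% |
| 10 | 0.05 | 1.45 | 1.20 | 96.8% |
| 10 | 0.10 | 1.90 | 1.38 | 93.8% |
| 10 | 0.20 | 2.80 | 1.67 | 87.6% |
| 10 | 0.30 | 3.70 | 1.92 | 82.0% |
| 12 | 0.30 | 4.30 | 2.07 | 78.6% |

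Cleavage and embryo quality may use fertilised oocytes or embryos as denominator, so their m would be smaller. With m = 3, DE is 1.2 at ICC 0.10 and 1.6 at ICC 0.30, and coverage is 98.1% and 95.8%.

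**Does the Poisson fallback help?** Not unless its variance is clustered on the woman. In an unadjusted two-arm comparison with M oocytes and event proportion p in an arm, the observation-level robust variance of log p is Mp(1 − p)/(Mp)² = (1 − p)/(Mp). That is exactly the binomial variance.

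**Simulation check.** The simulation used 140 women per arm, no treatment effect, beta-binomial data and 3,000 runs per scenario. Cluster sizes varied (negative binomial, mean about 10, shape 4), except that implantation had two embryos for every woman.

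| Event proportion | Mean m | ICC | Unclustered RR | Woman-clustered RR | Per-woman mean difference |
|---|---|---|---|---|---|
| 0.65 | 10 | 0.05 | 96.2% | 99.2% | 99.1% |
| 0.65 | 10 | 0.10 | 90.7% | 98.6% | 98.9% |
| 0.65 | 10 | 0.20 | 82.6% | 98.7% | 98.7% |
| 0.08 | 10 | 0.10 | 91.0% | 98.6% | 98.9% |
| 0.30 | 2 (fixed) | 0.30 | 97.9% | 99.0% | 98.9% |

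With a mean of 10, unclustered coverage falls below the first table because cluster sizes vary. The size variance is 10 + 100/4 = 35, so the squared coefficient of variation is 0.35 and DE becomes 1 + (1.35·10 − 1)·ICC. At ICC 0.10 this is 2.25 and coverage 91.4%, close to the simulated 90.7%.

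**The case against.** The strongest reply is that the protocol never makes the oocyte the unit of analysis. A reader might infer from section 8.1 that the five rates are committed to the risk-ratio models and that their intervals will therefore be too narrow. The text does not go that far. It lists rates without denominators and also provides linear and quantile regression for continuous secondary outcomes. If all seven listed outcomes were dichotomous, those provisions would have nothing to act on. They do have a use if each woman contributes her own proportion. The intention-to-treat sentence also speaks of outcomes for participants. On that reading there is no clustering error, and the per-woman column above confirms it. The robust variance is not said to be unclustered either; the section is simply silent. A statistical analysis plan, not shown here, may settle the unit.

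This makes the concern conditional but does not remove it. Whether an oocyte is normally fertilised is a yes/no result, and section 2 presents normal fertilisation (0.98), good-quality embryos (1.24), polyspermy (0.84) and implantation (1.80) as risk ratios. Someone following section 8.1 would naturally report the same measure by the named models. The section also goes beyond leaving detail open: it fixes the models, the fallback, the interval level and the one correlation to be handled. An analysis plan that followed it literally on the risk-ratio route would inherit the gap.

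It is also fair that the size rests on assumed inputs, and that implantation should not be grouped with the oocyte-based rates.

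**Conclusion.** The point holds in conditional form. If normal fertilisation, polyspermy, cleavage or embryo quality is analysed per oocyte or embryo with the stated risk-ratio models and no clustering on the woman, the nominal 99% intervals are too narrow. Coverage runs from about 98% (m = 5, ICC 0.05) to about 79% (m = 12, ICC 0.30). At the mild end the loss is modest; with about 10 oocytes and an ICC of 0.10 or more it is material. For implantation it is small, about 98% to 99%.

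Both m and the ICC are assumptions. The protocol permits an analysis with this fault and does not select one without it, which is less than saying that it prescribes the fault. Nor should a reader infer any doubt about the main result: live birth, its 95% interval and the 140 women per arm are unaffected.

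**What to change.** In section 8.1, state the denominator of each of the five rates, and state that outcomes counted per oocyte or embryo are analysed in one of two ways:

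- a log-link model (generalised estimating equations or Poisson) with the variance clustered on the woman, used in every case and not only when another model fails to converge, with 99% intervals from that variance; or
- one proportion per woman, analysed by the linear or quantile regression already in the plan.

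Choose one in advance for each outcome, because they answer slightly different questions: pooling over oocytes gives more weight to women with many oocytes, while a per-woman proportion weights women equally.

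The cost is a few sentences of text and wider intervals for these secondary outcomes. Under the assumptions above, standard errors would be about 1.10 to 2.07 times the unclustered ones for m = 5 to 12, and at most about 1.14 times for implantation. No change to the sample size or the primary analysis is needed.
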